A similar estimand as the estimand for the primary objective will be used for the secondary objectives.

Unless specified otherwise, safety assessments will be guided by an estimand comparing safety of LY3819469 doses with placebo irrespective of adherence to study intervention.

Overall Design

Study is a parallel, double-blinded, placebo-controlled, dose-finding, Phase 2 study of LY3819469 in participants with elevated Lp(a).

Approximately 254 participants will be randomized in a 1:2:2:2:2 ratio to 1 of the following arms:

- Arm A: 16-mg LY3819469, doses at randomization and Day 180
- Arm B: 96-mg LY3819469, doses at randomization and Day 180
- Arm C: 400-mg LY3819469, doses at randomization and Day 180
- Arm D: 400-mg LY3819469, dosed at randomization, placebo at Day 180
- Arm E: placebo, doses at randomization and Day 180

Brief Summary:

The purpose of this study is to measure difference in percent change from baseline in timeaveraged Lp(a) on over Days 60-180 with LY3819469 versus placebo in participants with elevated Lp(a).

Study details include:

- The study duration will be up to 20 months.
- The treatment duration will include doses at the randomization visit and at Day 180.

Study Population:

The study will include adults at least 40 years old. People in the study who are on particular medicines should stay on the same doses for the whole study. People who have had a major illness or surgery in the 3 months prior to the study will not participate. People who have certain abnormal laboratory values will not be included.

Number of Participants:

Approximately 254 participants will be randomly assigned to study intervention.

Intervention Groups and Duration:

All participants will receive a subcutaneous injection at the randomization visit and at Day 180 (Visit 7). LY3819469 is formulated at a concentration of 160 mg/mL.

	Arm A	Arm B	Arm C	Arm D	Arm E
Intervention Name	LY3819469	LY3819469	LY3819469	LY3819469 and Placebo	Placebo ^a
Dosage #1					
LY3819469 Solution (160mg/mL)	16 mg (0.1 mL)	96 mg (0.6 mL)	400 mg (2.5 mL)	400 mg (2.5 mL)	_
Placebo (0.9% sodium chloride solution for injection)	_	_	_	_	Placebo ^a
Dosage #2					
LY3819469 Solution (160mg/mL)	16 mg (0.1 mL)	96 mg (0.6 mL)	400 mg (2.5 mL)	_	_
Placebo (0.9% sodium chloride solution for injection)	_	_	_	Placebo ^b	Placebo ^a
Route of Administration	SC injection	SC injection	SC injection	SC injection	SC injection

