1.2. Schema

1.3. Schedule of Activities (SoA)

Period I - Optional Prescreening: The study includes an optional prescreening visit (Visit 601) as a simple way for sites to determine whether participants meet Lp(a) criteria, as assessed by a central laboratory assessment, before the full screening activities are initiated at Visit 1. If the participant has not had Lp(a) measured before or is unknown, the prescreening visit should be completed. The prescreening visit can be conducted at the study site, or remotely, for example, at a mobile healthcare or alternate laboratory. The prescreening activities will be described in an appropriate informed consent form (ICF). Informed consent for the prescreening activities will be obtained, a participant identification number will be assigned, and sample for the Lp(a) prescreening laboratory test will be obtained. The optional prescreening visit can be repeated 1 time (no more) per participant if the investigator believes the participant would meet criteria at a later time, with a minimum of 4 weeks between visits. Repeated sampling in the prescreening is opted for, central laboratory testing for Lp(a) is still required as part of the screening procedures conducted at Visit 1. Participants with Lp(a) <175 nmol/L at Visit 1 will not be eligible for enrollment, despite their values in prescreening. A prescreening visit occurring longer or shorter than 21 days (3 weeks) from screening will not be considered a protocol deviation.

Period II - Screening: Visit 1 procedures may be conducted over more than 1 day as long as all activities are completed prior to Visit 2.

Period III - Treatment and Assessment Period: All procedures (screening and baseline) need to be completed prior to the first dose of study intervention. For an early discontinuation (ED) from the study intervention that occurs before the last visit in treatment period, see the activities listed for ED in this table.

	Period I - Pre- Screening	Period II - Screening			Per	riod I	II T	reatm		Participants are required to fast before Visits 1-12. See Section 5.3.1. If a participant arrives not fasted, schedule the laboratory draw for another date.					
Visit number	601	1	2	3	4	5	6	7	8	9	10	11	12	ED	
Days from randomization	≤42	≤21		15	30	60	120	180	210	240	300	360	540		Visit 1 procedures may be conducted over more than 1 day if all activities are completed within the allowable visit tolerance.

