	Period I - Pre- Screening	Period II - Screening			Per	riod I	II T	reatm	Participants are required to fast before Visits 1-12. See Section 5.3.1. If a participant arrives not fasted, schedule the laboratory draw for another date.						
Visit number	601	1	2	3	4	5	6	7	8	9	10	11	12	ED	
Days from randomization	≤42	≤21		15	30	60	120	180	210	240	300	360	540		Visit 1 procedures may be conducted over more than 1 day if all activities are completed within the allowable visit tolerance.
Visit interval tolerance (days)	See Section 1.3	—		±3	±3	±3	±7	±7	±7	±7	±7	±7	±14		
Vital signs		Х	x	X	X	Х	х	х	х	х	х	х	х	х	Includes pulse rate and blood pressure measured after participant has been sitting at least 5 minutes and before ECG tracing and collection of blood samples for laboratory testing.
Physical examination		Х											х	Х	The physical examination is performed (excludes pelvic, rectal, and breast examinations unless clinically indicated).
Symptom- directed physical assessment								Х							Symptom-directed physical assessment will be conducted at the discretion of the PI or qualified personnel, per local regulations, as indicated based on participant status and standard of care.
12-Lead ECG (local)		Х						X				X	X	X	Collect single, local ECG prior to collection of blood samples for laboratory testing, including PK samples. Participants should be supine for approximately 5 to 10 minutes before ECG collections and remain supine but awake during the ECG collection. ECGs may be repeated at the PI's discretion at any visit. See Section 8.2.1.

	Period I - Pre- Screening	Period II - Screening			Pei	riod I	11 T	reatmo		Participants are required to fast before Visits 1-12. See Section 5.3.1. If a participant arrives not fasted, schedule the laboratory draw for another date.					
Visit number	601	1	2	3	4	5	6	7	8	9	10	11	12	ED	
Days from randomization	≤42	≤21	_	15	30	60	120	180	210	240	300	360	540		Visit 1 procedures may be conducted over more than 1 day if all activities are completed within the allowable visit tolerance.
Visit interval tolerance (days)	See Section 1.3			±3	±3	±3	±7	±7	±7	±7	±7	±7	±14		
Laboratory Tests and Sample Collections															
Hematology		Х			Х	Х		Х	Х	Х		Х	Х		
Clinical chemistry		Х	Х	Х	Х	Х		Х	Х	Х		Х	Х	Х	
Lipid panel		Х	Х			Х		Х		Х		Х	Х	Х	
Urinalysis		Х				Х		Х		Х		Х	Х	Х	
UACR		Х				Х		Х		Х		Х	Х	Х	
Serum pregnancy		Х													Females only.
FSH		Х													Optional; performed as needed to confirm postmenopausal status. See Appendix 10.4.

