TSH		Х													
HbA1c		Х						Х				Х	Х	Х	
Lp(a)	Х	Х	Х	Х	Х	Х	Х	Х	Х	Х	Х	Х	Х	Х	
ApoB		Х	Χ			Х	Х	Х	Χ	Х	Х	Х	Х	Х	
hsCRP		Х	Х			Х	Х	Х	Х	Х	Х	Х	Х	Х	
HIV screening test		Х													

	Period I - Pre- Screening	Period II - Screening			Per	riod I	II T	reatm		Participants are required to fast before Visits 1-12. See Section 5.3.1. If a participant arrives not fasted, schedule the laboratory draw for another date.					
Visit number	601	1	2	3	4	5	6	7	8	9	10	11	12	ED	
Days from randomization	≤42	≤21		15	30	60	120	180	210	240	300	360	540		Visit 1 procedures may be conducted over more than 1 day if all activities are completed within the allowable visit tolerance.
Visit interval tolerance (days)	See Section 1.3	—		±3	±3	±3	±7	±7	±7	±7	±7	±7	±14		
HCV screening test		Х													If HCV antibody test is positive, it must be followed by an HCV RNA test. See Section 8.2.5.
HBV screening test		Х													If HBsAg is negative and HBcAb is positive, further testing with HBV DNA is required. If the screening HBV DNA is negative, the participant is not excluded. See Section 8.2.4.
eGFR		Х				Х		Х		Х		Х	Х	Х	Calculated using CKD-EPI method.
Postdose PK sample			x					х							 Visit 2: Collect 2 samples. 0.5 hours postdose 4-9 hours postdose (minimum 2 hours) Visit 7: Collect 1 sample. 1. 24-36 hours postdose, will require participant to return 1 day after Visit 7.
Immunogenicity (ADA)			Р	Х	Х		Х	Р		Х		Х	Х	Х	Visit 2 and 7 will be collected predose.
PK sample for immunogenicity				X	X		X	Р		x		X	X	X	Collect a time-matched PK sample for all scheduled and unscheduled immunogenicity samples. Visit 7 will be collected predose.

	Period I - Pre- Screening	Period II - Screening			Per	iod II	(I T)	reatme		Participants are required to fast before Visits 1-12. See Section 5.3.1. If a participant arrives not fasted, schedule the laboratory draw for another date.					
Visit number	601	1	2	3	4	5	6	7	8	9	10	11	12	ED	
Days from randomization	≤42	≤21		15	30	60	120	180	210	240	300	360	540		Visit 1 procedures may be conducted over more than 1 day if all activities are completed within the allowable visit tolerance.
Visit interval tolerance (days)	See Section 1.3	—		±3	±3	±3	±7	±7	±7	±7	±7	±7	±14		
Stored Samples (On dosing days, collect samples before dosing	
Optional genetics sample			X												Sample can be obtained at or after the specified visit. See Appendix 10.5.
Exploratory biomarker samples			X			X		Х		Х		Х	х		
Randomization and Dosing															

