4.8.7.4. Renal Safety

Two shift tables examining renal function will be created: i) a min-to-min shift table of estimated glomerular filtration rate (eGFR) estimated by the Chronic Kidney Disease Epidemiology Collaboration (CKD-EPI) equation with unit mL/min/1.73 m², using categories ($<30, \geq 30$ to $<45, \geq 45$ to $<60, \geq 60$ to <90, and ≥ 90 mL/min/1.73 m²), and ii) max-to-max shift table of urine albumin-to-creatinine ratio (UACR), using the categories UACR <30 g/kg, 30 g/kg \leq UACR

 \leq 300 g/kg, and UACR >300 g/kg (respectively, these represent normal, microalbuminuria, and macroalbuminuria).

Mixed model repeated measure analyses for eGFR and UACR will be provided. Log transformation will be performed for UACR.

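### As scheduled, the eGFR analyses have one value before the first dose and none until about 60 days after each dose, although creatinine already drawn at Visits 2, 3, 4 and 8 could supply more

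*Protocol*

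**What the plan says.** In the Schedule of Activities (Protocol 1.3) the eGFR row carries the comment "Calculated using CKD-EPI method". Set against the visit header, its seven marks fall at Visits 1, 5, 7, 9, 11, 12 and ED. The chemistry row reads "Clinical chemistry Х Х Х Х Х Х Х Х Х Х Х". Its eleven marks fall at the same visits plus Visits 2, 3, 4 and 8. Protocol 10.2 lists creatinine in the chemistry panel and lists eGFR among the calculations generated by the sponsor's designated laboratory, so eGFR needs no tube of its own.

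On dosing, Protocol 1.1 says "All participants will receive a subcutaneous injection at the randomization visit and at Day 180 (Visit 7"). On the order of events at Visit 2, Protocol 1.3 says "All procedures (screening and baseline) need to be completed prior to the first dose of study intervention", which makes the Visit 2 chemistry a predose sample.

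SAP 4.8.7.4 plans two eGFR analyses. One is "a min-to-min shift table of estimated glomerular filtration rate (eGFR) estimated by the Chronic Kidney Disease Epidemiology Collaboration (CKD-EPI) equation", cut at 30, 45, 60 and 90 mL/min/1.73 m². The other is a repeated-measures model: "Mixed model repeated measure analyses for eGFR and UACR will be provided". The section lists no visits. Neither document says that eGFR will be derived from creatinine at Visits 2, 3, 4 or 8.

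**The concern.** The sponsor chose to draw chemistry early after each dose and again just before the first one. The dedicated renal analysis, as scheduled, uses none of those four draws. Two things follow.

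- A fall in eGFR that recovers within about 60 days of a dose has no scheduled value through which to reach either eGFR analysis in SAP 4.8.7.4.
- A min-to-min table is meant to compare the lowest of several baseline values with the lowest of several later ones. With one scheduled eGFR before the first dose, the baseline minimum is a single reading, taken up to 21 days before randomization. The minimum of five later readings will tend to fall below it even if nothing has changed.

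The sample size is justified partly by the safety data it yields (Protocol 9.5, SAP 5), so it makes sense to use the samples that are taken.

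**Working it through.** **Step 1: compare the two schedule rows (Protocol 1.3).**

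| Visit (day) | Chemistry, incl. creatinine | eGFR |
|---|---|---|
| 1 (screening, up to 21 days before) | yes | yes |
| 2 (randomization, dose 1) | yes, predose | no |
| 3 (Day 15) | yes | no |
| 4 (Day 30) | yes | no |
| 5 (Day 60) | yes | yes |
| 7 (Day 180, dose 2) | yes | yes |
| 8 (Day 210) | yes | no |
| 9 (Day 240) | yes | yes |
| 11 (Day 360) | yes | yes |
| 12 (Day 540) | yes | yes |
| ED | yes | yes |

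Chemistry visits without eGFR are 2, 3, 4 and 8. Leaving ED aside, scheduled eGFR values number 1 before the first dose and 5 after it. Adding the four visits gives 2 and 8.

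**Step 2: time from dose to first scheduled eGFR, with visit windows (±3 days at Visits 3 and 5, ±7 at Visits 7, 8 and 9).**

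- Dose 1, as scheduled: Day 60, range 57 to 63. With the change: Day 15, range 12 to 18.
- Dose 2, as scheduled: 240 − 180 = 60 days, range (240 − 7) − (180 + 7) = 46 to (240 + 7) − (180 − 7) = 74. With the change: 210 − 180 = 30 days, range (210 − 7) − (180 + 7) = 16 to (210 + 7) − (180 − 7) = 44.

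**Step 3: drift in the min-to-min table when nothing changes.** Assume that a participant's values are independent, normal and equally variable around an unchanged level, and that only scheduled values are used. The expected minimum of n standard normal values is 0 for n = 1, −0.564 for n = 2, −1.163 for n = 5 and −1.424 for n = 8. The expected apparent fall, in within-person SDs, is the expected baseline minimum less the expected postbaseline minimum:

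- As scheduled (1 versus 5): 0 + 1.163 = 1.163.
- Visit 2 baseline added only (2 versus 5): −0.564 + 1.163 = 0.599.
- Visit 2 and the three later visits added (2 versus 8): −0.564 + 1.424 = 0.860.

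The whole change removes (1.163 − 0.860) / 1.163 = 26% of the drift. The extra later looks give back 0.860 − 0.599 = 0.261 of the 0.564 gained from the second baseline value.

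Neither document gives the within-person SD of eGFR. Over an assumed range, in mL/min/1.73 m²:

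| Assumed SD | As scheduled (1.163 × SD) | With the change (0.860 × SD) |
|---|---|---|
| 4 | 4.7 | 3.4 |
| 6 | 7.0 | 5.2 |
| 8 | 9.3 | 6.9 |

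**Step 4: which baseline applies.** SAP 4.1 defines baseline as the last nonmissing value up to the randomization visit and before the first dose, which admits a Visit 2 predose sample. Row 1.3 of Table EZEB.4.3, for change in laboratory values, asks for a value from before the calendar date of the first dose. Read literally, that shuts out a sample taken earlier on the dosing day. For treatment-emergent abnormal values, SAP 4.1 takes the most extreme of all baseline-period values. An eGFR derived at Visit 2 would meet all three rules, so the SAP needs to say how it is treated.

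**The case against.** The best reply is that early renal information is already analysed. Creatinine is part of the chemistry panel, and SAP 4.8.6 gives laboratory summaries by nominal visit, a shift table with Fisher's exact test and a listing of abnormal findings. Protocol 8.2.2 also requires investigators to review results and report clinically relevant changes as adverse events. A fall in creatinine-based eGFR is a rise in creatinine in the same sample. This stands. A reader might infer that an early renal effect would go unseen, and the documents do not support that. What remains is narrower: the 4.8.6 tables use laboratory limits and not the eGFR categories, so they do not replace the tables in 4.8.7.4.

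Second, the SAP does not rule out eGFR at other visits. Section 4.8.7.4 names none, and an ED or unscheduled test could give an individual an earlier value. That also stands, and it is why the point concerns what is scheduled and planned.

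Third, a reader might infer that the single baseline value distorts the comparison with placebo or hides a real difference. All arms share one schedule, so the drift affects them alike and need not bias the comparison. No category-shift rate or loss of sensitivity has been calculated, so a claim of dilution is not established.

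Fourth, the gain is limited. Nothing before Day 15 is recovered after dose 1, and the first look after dose 2 is still about 30 days out. UACR follows the same visits as eGFR and cannot be derived from creatinine.

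**Conclusion.** The point holds as a low-severity, no-cost improvement to SAP 4.8.7.4. The gap between the two schedule rows is exact and needs no assumption: four chemistry visits have creatinine but no scheduled eGFR. Deriving eGFR there brings the first look forward by 45 days after dose 1 (Day 60 to Day 15) and by 30 days after dose 2 (Day 240 to Day 210).

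The effect on the min-to-min table is secondary. The drift falls from about 1.16 to 0.86 within-person SDs if values are independent, and any translation into mL/min/1.73 m² rests on an assumed SD. It should not be used to argue that the planned comparison with placebo is invalid.

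**What to change.** Add to SAP 4.8.7.4:

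- CKD-EPI eGFR is derived from every central-laboratory serum creatinine, including Visits 2, 3, 4 and 8.
- The repeated-measures model uses scheduled visits only, in line with the SAP's exclusion of unscheduled values from continuous laboratory analyses (note to Table EZEB.4.3). Its baseline is the last nonmissing predose value, normally Visit 2. Keeping the last-nonmissing rule preserves the fallback to screening when Visit 2 is missing.
- The min-to-min shift table uses all scheduled and unscheduled values, with the minimum of all baseline-period values as baseline.

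Clarify row 1.3 of Table EZEB.4.3 so that a predose sample taken on the day of the first dose counts as baseline. State which baseline eGFR feeds the subgroup split at 60 mL/min/1.73 m² in SAP 4.9, since the new Visit 2 value could change it.

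The cost is a short SAP edit and programming. No visit, sample or clinical rule changes. The UACR gap remains.

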2.1. Study Rationale

Elevated Lp(a) is recognized as an important risk factor of cardiovascular disease; there are currently no approved pharmaceutical interventions for lowering Lp(a). LY3819469 is an siRNA, that decreases Lp(a) formation and has been shown to reduce Lp(a) in preclinical studies. In Phase 1 Study J3L-MC-EZEA (EZEA) with single doses of LY3819469, Lp(a) was significantly decreased and no safety issues were identified. This Phase 2 study aims to investigate the impact of a range of LY3819469 doses on Lp(a) level and on safety in a larger population of participants with elevated Lp(a) to enable Phase 3 development of this compound.

2.2. Background

2.2.1. Introduction to Lp(a)

Lp(a) is an atherogenic lipoprotein consisting of a low-density lipoprotein particle linked via a disulfide bond to Apo(a) (see Figure 1).

Apo(a) is a protein found in new-world monkeys, great apes, and humans (Utermann 1989). The protein, encoded by the LPA gene, includes 10 unique units of kringle IV repeats; the first and third through tenth are present in single copies while the second is present in variable copy numbers (1 to <50). Additionally, the protein includes a kringle V and a protease-like domain that is not biologically active (Dubé et al. 2012; Kronenberg and Utermann 2013; Tsimikas 2017).

Abbreviations: Apo(a) = apolipoprotein(a); ApoB = apolipoprotein b; LDL = low-density lipoprotein; Lp(a) = lipoprotein(a).

Figure 1. Representation of Lp(a) particle.

Lp(a) contains oxidized phospholipids. Plasma levels of Lp(a) are genetically determined. Single-nucleotide polymorphisms (SNPs) of the LPA gene are associated with higher or lower Lp(a) levels; for example, rs10455872 and rs3798220 are associated with increased Lp(a) (Clarke et al. 2009; Li et al. 2011). Additionally, the number of kringle IV2 repeats determines protein size, which is inversely proportional to plasma concentration and mass of Lp(a); larger Apo(a) size is associated with lower concentrations of Lp(a). Despite this genetically induced variability in Lp(a) concentrations between individuals, intra-patient variability in Lp(a) is low and is not thought to be materially impacted by diet, environmental factors, or exercise (Schmidt et al. 2016). However, Apo(a) is an acute-phase reactant, and Lp(a) increases, for example, after surgery, myocardial infarction, and infection (Maeda et al. 1989; Noma et al. 1994; Min et al. 1997).

2.2.2. Elevated Levels of Lp(a) Are Associated with Increased Risk of Cardiovascular Disease

Lp(a) particles are thought to exert adverse cardiovascular effects through atherogenic, inflammatory, and possibly pro-thrombotic activity (Tsimikas 2017).

In a meta-analysis of 36 studies, Lp(a) was associated with risk for nonfatal myocardial infarction or coronary death (Emerging Risk Factors Collaboration et al. 2009). In studies of LPA gene KIV2 repeats or SNPs, genetic variants conferring higher levels of Lp(a) were found to be related to risk for myocardial infarction and coronary disease in Mendelian randomization and genome-wide association studies (Clarke et al. 2009; Kamstrup et al. 2009). In a study including data from the United Kingdom (UK) Biobank, 7 genome-wide association studies, and LPA sequencing, Lp(a) was associated with risk of coronary heart disease, stroke, chronic kidney disease, aortic valve stenosis, heart failure, and peripheral vascular disease (Emdin et al. 2016).

The American Heart Association and American College of Cardiology Guideline on the management of blood cholesterol defined $Lp(a) \ge 50 \text{ mg/dL}$ or $\ge 125 \text{ nmol/L}$ as risk enhancing in 2018 (Grundy et al. 2019). Elevated Lp(a) > 50 mg/dL was present in 24% of samples from a reference laboratory and 29.2% of samples from a tertiary care center (Varvel et al. 2016). The estimated prevalence of Lp(a) > 60 mg/dL is 64 million in the United States, 150 million in Europe, and 1.4 billion worldwide (Tsimikas and Stroes 2020).

2.2.3. Available Treatments

Lipid apheresis is approved and used in some geographies for patients with elevated Lp(a) (Jaeger et al. 2009; Nugent et al. 2020). Proprotein convertase subtilisin/kexin type 9 (PCSK9) inhibitors, alirocumab, evolocumab, and inclisiran, reduce Lp(a) by approximately 25% (Robinson et al. 2015; Sabatine et al. 2015; Stoekenbroek et al. 2019), and prescription-strength niacin also produces 15% to 25% reductions in Lp(a) (AIM-HIGH Investigators 2011; HPS2-THRIVE Collaborative Group 2014), but are not approved treatments for Lp(a) reduction. Novel treatments to reduce Lp(a) are under investigation, including an antisense oligonucleotide (pelacarsen), and 2 siRNA therapies (olpasiran and SLN360), which have been shown to lower Lp(a) concentrations in clinical trials (Viney et al. 2016; Tsimikas et al 2020; Ference 2022; Koren et al. 2022; Nissen et al. 2022).

2.2.4. Introduction to LY3819469

LY3819469 inhibits the production of Apo(a) by causing degradation of LPA mRNA through the siRNA mechanism. LY3819469 reduces steady-state levels of Apo(a) protein in a mouse model transgenic for human Apo(a), and Lp(a) in cynomolgus monkeys that endogenously express Lp(a).

Nonclinical toxicology studies of LY3819469 showed no notable adverse drug effects.

In Phase 1 Study EZEA of participants treated with single LY3819469 doses up to 608 mg, Lp(a) was lowered and no notable adverse drug effects were observed.

Efficacy will be determined by measuring circulating levels of Lp(a) in this Phase 2 study to enable dose selection for Phase 3 study.

